## Study Type and Performance Site Information

**Type of study:**

**Standard or Expedited**

Exempt

Grant Review/Umbrella Review for funds release

Comparative Effectiveness Research

Non-Human Subject Determination

Quality Improvement/Non-Research Determination

Study reviewed by another IRB

Coordinating Center ONLY

**Please indicate which Committee is most appropriate to review your project:**

**Social and Behavioral Sciences**

Health Sciences

**Are there sites in this study in which the PI is responsible other than Vanderbilt University or Vanderbilt University Medical Center, including all VUMC clinics and hospitals?**

**Yes**

No

**Are there any international sites involved?**

Yes

**No**

**Are the sites "Engaged in the Research"?**

yes

**no**

both engaged sites and not engaged sites

**Are any of these sites international?**

Yes

**No**

Date of IRB Approval: 04/09/2018

**Institutional Review Board**

**Is this project cancer-related?**

[ ] Yes

**[x] No**

Date of IRB Approval: 04/09/2018

**Institutional Review Board**

## Study Purpose and Description

**Provide a brief abstract of the study in lay language. The IRB Committees are comprised of scientists with varied backgrounds, non-scientists, and community members.**

This IRB application addresses the second of three aims for our overall research plan: to evaluate a mobile-phone delivered medication adherence intervention (called REACH; Rapid Education/Encouragement And Communications for Health) and test intervention effects on adherence and glycemic control among low income adults with type 2 diabetes mellitus (T2DM) receiving primary care at Federally Qualified Health Centers (FQHCs) or VUMC. In addition, family-focused components (called FAMS; Family-focused Add-on to Motivate Self-care) are integrated with the larger REACH intervention, and include diabetes coaching, goal-focused text messages delivered to the patient, and supplemental text messages delivered to an identified adult family member. We will evaluate the effects of the supplemental, family-focused intervention on family members' supportive and obstructive behaviors, patients' diabetes self-efficacy, and patients' adherence to diet and exercise. (Aim 1, to improve the content and functionality of an existing mobile phone-delivered medication adherence promotion intervention for consistency with the Information-Motivation-Behavioral skills model and clear health communication strategies, and test for usability and acceptability with patients, received approval [see IRB #140562] in April 2014.)

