**Institutional Review Board**

## Data and Safety

**Describe how the risks to participants are minimized (e.g., screening to assure appropriate selection of participants, identify standard of care procedures, sound research design, safety monitoring and reporting).**

Risks to participants are minimized through study procedures, including screening to assure appropriate selection of participants, the use of standard of care procedures (e.g., routine A1c laboratory testing), and safety monitoring and reporting. KSP will screen all patients for eligibility. Trained RAs will review patients' electronic medical record (EMR) to confirm age (18 years or older), a diagnosis of T2DM, and a prescription for daily diabetes medication, defined as a daily medication to control blood sugar. In addition, trained RAs will ensure risks are minimized by confirming patients are able to provide written informed consent, do not have certain impairments (e.g., visual, hearing, speech) that may effect their ability to participate in this research, and are able to receive, read, and respond to text following RA instruction (see REACH RCT Eligibility and Consent).

Participants will receive an A1c blood test at enrollment/baseline, 3-, 6-, 12-, and 15-month assessments. The testing of A1c on a 3-month interval basis is the current standard of care. RAs will work with clinics and patient participants to schedule assessments in line with routine clinic visits to minimize unnecessary patient or provider burden. Participants may experience pain, discomfort, and bruising as a result of the A1c blood test; however these are the risks of this test, which are conducted routinely for patients with uncontrolled diabetes. During the informed consent process, patients will be told they may experience discomfort from thinking about, reporting, and/or discussing how they manage their diabetes, and certain health information will be sent to their cell phones via text message, which may include medication names or information about how to access their A1c test results. If they share or lose their phone, they risk disclosing this information to someone else. Family member participants will not be provided with any health information, but the patient's name will be disclosed along with health-related language that may implicate the patient.

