## Recruitment

### Describe the specific steps to be used to identify and/or contact prospective participants. (If applicable, also describe how you have access to lists of potential participants.)

Recruitment methods will include the use of interest cards, flyers and brochure, and referrals from healthcare providers and clinic staff, and in-person contact with patients in the clinic waiting room or at clinic and community events (see RCT Interest Cards, RCT Study Contact Cards, Recruitment Flyer with Tabs, and RCT Appointment Reminder Cards).

We will also contact potential participants through a letter via postal mail and e-mail. This also will allow us to contact patients who aren't in the clinic as often (e.g., every six months) so thus would be unlikely to come in contact with KSP on-site or fill out an interest card. Our partnered clinics will provide a listing of potential participants based on their EMR queries (e.g., with parameters related to our inclusion criteria such as patients with Type 2 diabetes and on at least one daily diabetes medication). Potential participants will be sent a letter via postal mail (see Participant Recruitment Letters). We are no longer pursuing recruitment via e-mail at Neighborhood Health. For our other partnering clinics, those potential participants who have an e-mail listed as a contact in their EMR will be sent an e-mail (see Participant Recruitment Email). E-mails will be sent from [contact] (which is only accessible to KSP) or a clinic e-mail address, if preferred by the clinic.

Each clinic reviewed and approved the letter and e-mail for use with their patients. Per the request of Neighborhood Health, the mailed recruitment letter is now using an opt-in approach. The letter describes the research, and explains how to call the REACH Helpline to opt-in. Only those Neighborhood Health patients that opt-in are contacted further by KSP. For our other partnering clinics, the letter also briefly describes the research opportunity, and then explains that a KSP will contact them about participating in the study. For those who are not interested and do not want to be contacted by KSP, we provide instructions on how they can opt-out using the REACH Helpline. Those participants who opt out will not be further contacted for study participation by KSP.

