We will also use a brief recruitment text (see Recruitment Text) to send participants identified from clinic lists so they can respond with a time that is convenient for them for us to call and tell them more about the study. This will help reduce the amount of attempts and back and forth calls in trying to speak with the potential participant.

We may use text messages to correspond with participants who are enrolled in the study. Typically, we use phone calls to communicate with participants about study information (e.g., remind them about upcoming study appointments, confirm receipt of a mailed survey). We will use text messages as a back-up method of communication in our attempts to reach participants about relevant study information.

For potential participants at Faith Family Medical Center, clinic pharmacists will also give patients a half-page insert when they pick up their diabetes medication at the clinic pharmacy. Additionally, we will recruit participants from our previous research studies who indicated they would like us to contact them for future research studies. These individuals will be contacted by their preferred method (e.g. cell phone), and invited to participate.

Patients can also contact research staff via the REACH Helpline if they are interested in participating after learning about REACH at their clinic (see REACH Recruitment Script).

VUMC patient recruitment: We will also locate potential participants meeting eligibility criteria at Vanderbilt locations through specific tools including subject locator, my research at vanderbilt (MRAV), and research derivative. Subject Locator will be used as a recruitment tool to identify potential research subjects based on available in VU clinical systems (e.g. STAR Panel, WizOrder, Clinic Scheduling). The Subject Locator program is part of a toolset available through VICTR that enables teams to specify inclusion/exclusion criteria for a specific study. The inclusion/exclusion criteria are codified for computable use and combined with data coming through VU Clinical Systems to proactively identify individuals who might qualify for a study. KSP will use Subject Locator to identify patients who met eligibility criteria. KSP will then conduct EHR review to confirm the patient met eligibility criteria. We then e-mail or mail all identified patients an

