**Date of IRB Approval: 04/09/2018**

**Institutional Review Board**

IRB-approved letter from [name] stating that research staff will contact them about the study unless they respond via e-mail or phone to opt-out. 7-10 days after the e-mails and letters are sent, KSP will call patients who did not opt-out to tell them about the study. We have approval to contact these patients from the Medical Director of Vanderbilt Primary care, and the primary care physicians at the clinics we are recruiting from.

Once enrolled, any participants randomized to FAMS will be asked if they want to invite an adult family member to participate. They can elect to invite a family member by providing the person's name and mobile phone number. KSP will then contact the family member to describe the study and formally invite them to participate (see also FAMS Recruitment and Enrollment Script Family Members).

Those participants who complete a follow-up survey electronically or via mailed paper copy will receive their materials along with a cover letter that explains the study components. KSP will fill out the information needed. Because this is a long study with several components, this letter and figure help to reiterate key points of the study, and we hope, also contribute to better retention. KSP will use to appropriate form based on how the participant will be completing the survey (e.g., online, mailed paper survey) and which items are needed for the timepoint (e.g., A1c, survey, both), fill it out with the applicable information, and these letters will be included when sending the online or paper follow-up survey materials.

**Identify the criteria for inclusion and exclusion and explain the procedures that will be used to determine eligibility. If psychiatric/psychological assessments will be conducted (e.g., depression or suicidal ideation screenings), state who will administer, his/her experience, and how risks will be managed.**

Patient inclusion criteria includes adults aged 18 years and older (per participant report and confirmed by a trained RA following informed consent); individuals with a diagnosis of T2DM; patient at a participating health center (Faith Family Medical Clinic, The Clinic at Mercury Courts, Vine Hill Community Clinic, Priest Lake Family & Women's Health Center, Neighborhood Health Clinics, and VUMC; see Faith Family, [name], and UCHS Letters of Support); and current treatment with oral and/or injectable daily diabetes medication.

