Patient exclusion criteria includes non-English speakers; individuals reporting they do not have a cell phone; individuals unwilling and/or not able to give informed consent; individuals whose most recent A1c value, within 12 months, is <6.8%; individuals with unintelligible speech, a severe hearing impairment, or visual impairment; individuals reporting that a caregiver administers their diabetes medication; individuals unable to pass cognitive screening for eligibility; and individuals who cannot receive, read, and respond to a text message after instruction from a trained RA.

Upon recruitment, KSP will ask participants questions to pre-screen for eligibility either via telephone or in-person. If an individual meets those criteria and is interested in participating, KSP then schedule a time to complete eligibility screening and, if eligible, proceed to enrollment. Eligibility screening includes: a brief cognitive screening measure and a series of text message exchanges to ensure the participant is able understand, send, and receive text messages (see REACH Eligibility and Consent).

Family member inclusion criteria includes adults aged 18 years and older (per participant report and confirmed by a trained RA following informed consent); someone identified by the participant as part of their family (biologically or legally, or a close friend or roommate who is involved in the patients' daily routine).

Family member exclusion criteria includes non-English speakers; individuals reporting they do not have a cell phone; individuals unwilling and/or unable to give informed consent; and individuals with unintelligible speech, a severe hearing impairment, or visual impairment.

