**Describe how the selection of participants is equitable in relation to the research purpose and setting.**

Given our study aims, this research does not require systematic procedures to ensure equitable selection. We will enroll adults with T2DM that are diverse with respect to age, gender, race, and ethnicity.

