**Please describe other:**

We will use Subject Locator to identify patients prior to upcoming appointments at Vanderbilt Primary Care clinics and send an opt-out letter or email. We may also contact patients via e-mail if indicated as a preferred method of contact on an interest card (see REACH Recruitment Email). We will send a recruitment e-mail (see Clinic Recruitment Letters) for those potential participants identified by one of our partnered clinics based on their EMR queries who have an e-mail contact listed in their EMR. Additionally, we will recruit patients through face-to-face communication in the waiting rooms of participating clinics, as well as at clinic or community events. Providers at participating clinics may also refer patients to the study, and patients can call the REACH Helpline to receive more information about participation (see REACH Recruitment Script).

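### Does a low income description in the protocol's abstract need an income rule in the eligibility criteria?

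*Protocol*

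**What the plan says.** The abstract in the protocol's Study Purpose and Description names adherence and glycemic control as the outcomes of the aim, and it places the test "among low income adults with type 2 diabetes mellitus (T2DM) receiving primary care at Federally Qualified Health Centers (FQHCs) or VUMC". The next sentences of the abstract bring in the family-focused FAMS component and its outcomes without mentioning income.

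The criteria themselves are under Recruitment. Patients must be adults with type 2 diabetes who attend a participating center, "and current treatment with oral and/or injectable daily diabetes medication". VUMC is listed beside the community clinics on equal terms. The exclusions begin "Patient exclusion criteria includes non-English speakers; individuals reporting they do not have a cell phone" and go on to consent, a recent A1c below 6.8%, sensory and speech impairments, medication given by a caregiver, cognitive screening and the ability to use text messages.

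The SAP names dietary behavior and physical activity as primary outcomes and diabetes self-efficacy as secondary. It compares REACH+FAMS with control at 3 and 6 months and does not define the population by income.

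**The concern.** In the abstract's sentence, low income applies to VUMC patients as well as to those at the FQHCs. At a community clinic serving disadvantaged patients, being a patient there might stand in for an income rule. A medical center's primary care clinics offer no such assurance, and the protocol sets no cap on their contribution. The trial as written could therefore enrol many VUMC patients who are not low income and still be described as a trial in low income adults.

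What would be at stake is applicability. The protocol's Background rests its case largely on patients of low socioeconomic status, and it says that such patients are more exposed to the harm done by obstructive family behavior. If the effect depends on income, a mixed sample under a low income description would mislead readers about whom the result concerns.

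**Working it through.** There is no figure in the plan to reproduce. The check is whether any step that selects patients uses income or a stand-in for it.

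| Step | Protocol location | What it selects on | Income term? |
|---|---|---|---|
| Inclusion | Recruitment | age, diagnosis, center, "and current treatment with oral and/or injectable daily diabetes medication" | none |
| Exclusion | Recruitment | opens "Patient exclusion criteria includes non-English speakers; individuals reporting they do not have a cell phone"; remainder as listed above | none |
| Record check by research assistants | Data and Safety | "to confirm age (18 years or older), a diagnosis of T2DM, and a prescription for daily diabetes medication" | none |
| Clinic record queries | Recruitment | "with parameters related to our inclusion criteria such as patients with Type 2 diabetes and on at least one daily diabetes medication" | none, but the parameters are only examples |
| VUMC search | Recruitment | "KSP will use Subject Locator to identify patients who met eligibility criteria" | none beyond the criteria above |
| VUMC timing | Recruitment, description of other methods | "We will use Subject Locator to identify patients prior to upcoming appointments at Vanderbilt Primary Care clinics" | none |
| Equity statement | Recruitment | "We will enroll adults with T2DM that are diverse with respect to age, gender, race, and ethnicity" | income not among the characteristics |

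So the factual part of the concern holds: no visible rule selects on income, and nothing visible substitutes for one at VUMC.

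Next, what depends on the phrase?

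1. **Enrolment.** Staff work from the inclusion and exclusion lists, and the record check and searches agree with them on income. Deleting the phrase from the abstract would change nobody's eligibility.
2. **Analysis.** The SAP's regression models use the baseline value of the outcome, with multiple imputation. No term, subgroup or analysis set depends on income.
3. **Validity.** Patients are randomised after consent and enrolment. Whatever the income mix, the comparison of arms is unbiased for the population enrolled.
4. **Conclusions.** The low income sentence concerns adherence and glycemic control. The SAP concerns diet, physical activity, self-efficacy and family or friend involvement. No planned conclusion in the SAP uses the phrase.

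Finally, how large could the applicability gap be? Let s be the share of the sample that is not low income, and d the relative amount by which the effect in that share falls short of the low income effect E.

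- Whole-sample effect = (1 − s)E + s(1 − d)E = E(1 − sd)
- Gap relative to E = s × d

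The documents give neither s nor d. As pure assumptions, s = 10% with d = 25% gives 0.10 × 0.25 = 2.5%, and s = 50% with d = 50% gives 0.50 × 0.50 = 25%. With d = 0 the gap is zero for any s. The spread comes from the chosen inputs and says nothing about this trial. The accrual goal of 525 (Subject Population(s)) does not narrow it, because no split by site is given.

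**The case for a change.** The strongest case for acting is that the form asks directly for inclusion and exclusion criteria, so an income rule belonged there if one existed. The VUMC tools apply those criteria, so as written they cannot select on income. FAMS patients are randomised from the same pool as REACH patients, so the absence of the phrase from the FAMS sentences does not really separate the two populations. The protocol also supplies a reason to expect effect modification: it links low socioeconomic status to greater harm from obstructive family behavior, and the SAP makes harmful family or friend involvement a targeted mediator. The correction would be one edit and one table.

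Much of this stands. The mismatch is real, and possible effect modification is a fair reason to want the income mix reported. But the argument shows only that readers should see who was enrolled. It does not show that a planned analysis or conclusion is wrong. The record is also incomplete on this very point. The eligibility and consent form, the survey and the study design sheet are named in the protocol but are not in the public copy, and the answer on whether a specific social group is targeted cannot be read. Within VUMC, the protocol speaks of the clinics being recruited from without saying how they were chosen. An income rule or a chosen subset of clinics may exist.

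A site-type covariate (VUMC versus the other centers) would not help. It does not measure income, it leaves the wording as it is, its gain in precision cannot be estimated from the documents, and it would be a late addition to models that the SAP describes as already run.

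**Conclusion.** No change to the plan is needed. The protocol's abstract describes the sample more narrowly than its criteria do, and the criteria govern. The consequence is confined to applicability: the effect on bias, type I error and power is nil, and the effect on whom the results describe cannot be sized from the documents and may be zero.

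This rests on two assumptions. The first is that the trial report describes the sample by the criteria and sites actually used. The second is that its baseline table includes income or insurance, as is usual for a trial with this rationale; the protocol mentions a demographic form, but its items are not visible. Analysts would do both as a matter of course, and neither needs an amendment.

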**Expected duration of the study.**

We expect to complete data collection by the end of 2019, but the study will remain open for analyses and manuscript writing/submissions for an additional five years.

**The IRB needs to understand how this study adds to the knowledge on this topic in order to be able to judge the risks and benefits to the research participants.**

## BACKGROUND

Medication nonadherence is a major public health problem with few solutions for patients with diabetes. Approximately 1 in 3 persons with T2DM are suboptimally adherent [1-3], and this rate is higher among low income racial/ethnic minorities with diabetes [4-7]. Medication nonadherence undermines treatment effectiveness, and in doing so, contributes to suboptimal glycemic control [4-6, 8], hospitalizations [3, 9-11], premature death, and considerable costs to the U.S. healthcare system [11, 12]. In our prior work with 314 diverse patients with low socioeconomic status [13], 79% reported less than perfect medication adherence and 66% had a hemoglobin A1c (A1c)  $\geq 7.0\%$ . Moreover, medication adherence was the only self-care behavior associated with glycemic control when adjusted for other self-care behaviors (e.g., diet, exercise, self-monitoring of blood glucose (SMBG)), highlighting the need to improve medication adherence in order to achieve glycemic control in low SES patient populations [13].

Recent evidence suggests African Americans (AAs) with diabetes are more likely than non-Hispanic Whites (NHW) to report lacking adherence-related information (e.g., not knowing the number of doses to take or what each medication is for) [14], motivation (e.g., believing medications do more harm than good and lacking social support for adherence) [14-16], and behavioral skills (e.g., forgetting doses and having difficulty obtaining refills) [14, 17, 18]. These barriers map onto a well-validated conceptualization of adherence behavior, the Information--Motivation--Behavioral skills (IMB) model [19], which informed effective medication adherence interventions among patients with other chronic conditions [20-23]. Yet of published intervention studies addressing medication adherence among patients with T2DM [24-41], only one [29] is theory-based, and there are no studies, to our knowledge, that used a theory with empirical support for the theory's tenants in a target population and/or pertaining to that population's medication adherence behavior, specifically. The IMB model of adherence [19] is validated in cross-sectional [42, 43] and intervention outcome research with patients with HIV and, separately, with patients who underwent heart surgery [20-23], and incorporates central components of other theoretical models (e.g., Social Cognitive Theory [44], Theory of Planned Behavior [45]).

Given increased rates of T2DM-related complications and mortality among minority groups and patients with low SES [46, 47], it is particularly critical to focus family interventions on at-risk patient populations who may need more support to maintain self-care and glycemic control [48, 49]. Such populations have higher rates of limited health literacy [50], life stressors [51-53], and depression [54, 55], making them more vulnerable to the detrimental effects of obstructive family behaviors on self-care and A1C [48, 49]. Interventions simply educating and/or involving families without working to reduce obstructive family behaviors may actually evoke less patient adherence [56-59]. We explored cross-sectional associations between diabetes-specific supportive and obstructive family behaviors and adults' T2DM self-care behaviors and A1C in the target population and found that family members' supportive and obstructive behaviors were each independently associated with more and less adherence to self-care, respectively [56].

